14.6. Secondary Analysis

Secondary efficacy analysis:

See section 14.5

14.7. Other Exploratory Analyses

Not Applicable.

14.8. Interim Analysis

Not Applicable.

14.9. Procedure for Handling Missing Data and Drop-Outs

Missing or spurious values will not be imputed. The count of missing values will be included in the summary tables and listings.

Subject dropout is expected to be one of the main reasons of missing data in this clinical trial. Past clinical trials don't provide the evidence that subject dropout is systematic or not-at-random. To evaluate the impact of missing data, sensitivity analysis will be conducted using multiple imputation methods if the proportion of subject dropout is greater than the 15%. The SAS/STAT procedures PROC MI and PROC MIANALYZE will be utilized with a parametric regression method used to make at least 5 imputations.

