3.3	Ocular Symptoms	Subjects will respond to a verbal open-ended symptoms questionnaire.	
3.4	Entrance Visual Acuity	
Record the distance and near Snellen visual acuity with the subjects' habitual correction in place (OD, OS, and OU) to the nearest letter. Subjects must read the smallest line until at least 50% of the letters are read incorrectly.
 
Note: Use the ETDRS 2000 Series Chart 1 or 2 near card placed at 40 cm to measure the Near visual acuity.
	
3.5	Lens Removal	Have the subject remove their habitual lenses and store in an approved storage solution.	
3.6	Biomicroscopy	
FDA Slit Lamp Classification Scale will be used to grade the findings and determine eligibility.
 
For the conjunctival redness [REDACTED] 0.5 unit increments will be used in the grading. Corneal Staining Assessment [REDACTED] will be graded in 1.0 increments.
 
If any of these slit lamp findings are Grade 3 or higher, the subject will be discontinued. If discontinued a final examination must be completed.
 
If the clearance of the fluorescein needs to be expedited, preservative-free rewetting drops or
	[REDACTED] [REDACTED] [REDACTED]

		saline may be instilled.	
3.7	Continuance	Determine whether the subject is eligible to continue in the study based on the examination findings.	

Visit 3: Treatment 2 Lens Fitting			
Step	Procedure	Details	
3.8	Lens Selection	Select the monovision power based on the lens power dispensed at Visit 1. Record the Test lens parameters (power and lot number).	
3.9	Lens Insertion	Subjects will insert the lenses themselves. If the lens is uncomfortable, inspect for damage and remove, reinsert or replace as necessary. Damaged lenses will be stored in labeled vial with sterile saline, and clearly differentiated from the other worn lenses that will be shipped back to the Sponsor. Complete the Quality Product Complaint form.	
3.10	Lens Settling	Allow the study lenses to settle for a minimum of 10 minutes.	
3.11	Determine Visual Satisfaction	Determine if the subject's vision is acceptable with the lenses. Allow the subject to look down a hallway or out of a window for distance vision assessments, and for them to read a book, magazine or similar for near vision. Note: If the subject's vision is unacceptable the subject will be discontinued. Complete the final evaluation. (No Modifications allowed)	

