14. STATISTICAL METHODS

14.1. General Considerations

All data summaries and statistical analyses will be performed using the Statistical Analysis System (SAS) software Version 9.4 (SAS Institute, Cary, NC). Throughout the analysis of data, the results for each subject/eye will be used when available for summarization and statistical analysis. Unscheduled visits will be summarized separately and will be excluded from the statistical analysis.

Summary tables (Descriptive statistics and/or frequency tables) will be provided for all baseline variables, efficacy variables and safety variables as appropriate. Continuous variables will be summarized with descriptive statistics (n, mean, standard deviation [SD], median, minimum and maximum). Frequency count and percentage of subjects or eyes within each category will be provided for categorical data.

Summaries will be presented by study lens type and will be performed separately by completion status (Safety Population or Per-Protocol Population). All analyses will be conducted on per-protocol population (see Section 14.3).

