14.3. Analysis Populations

Safety Population:

All subjects who were administered any test article excluding subjects who drop out prior to administering any test article. At least one observation should be recorded.

Per-Protocol Population:

All subjects who have successfully completed all visits and did not substantially deviate from the protocol as determined by the trial cohort review committee prior to database hard lock (Per-Protocol Population). Justification of excluding subjects with protocol deviations in the Per-Protocol Population set will be documented in a memo to file.

Intent-to-Treat (ITT) Population:

All subjects regardless of actual treatment and subsequent withdrawal from study or deviation from protocol. At least one observation should be recorded.

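### The drop-out sensitivity analysis in 14.9 names no population, and under 14.1 and 14.3 it would have no drop-outs to impute

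*Combined protocol and SAP*

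**What the plan says.** Section 14.9 states for the main analysis that "Missing or spurious values will not be imputed". It names drop-out as an expected main cause of missing data and says past trials give no evidence that it is systematic. To assess its effect, "sensitivity analysis will be conducted using multiple imputation methods if the proportion of subject dropout is greater than the 15" per cent. The method is PROC MI and PROC MIANALYZE, with "a parametric regression method used to make at least 5 imputations". No analysis population is named, and the denominator of the 15% is not defined.

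Section 14.1 says: "All analyses will be conducted on per-protocol population (see Section 14.3"). Section 14.3 defines that population as "All subjects who have successfully completed all visits and did not substantially deviate from the protocol". It also defines an ITT population, "All subjects regardless of actual treatment and subsequent withdrawal from study or deviation from protocol", but no analysis or summary in section 14 is assigned to it. Summaries, as opposed to analyses, are to be "performed separately by completion status (Safety Population or Per-Protocol Population").

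Section 8.2 allows a discontinued subject to be replaced, and lists failure to be dispensed because of poor vision, comfort or fit among the withdrawal reasons. In section 7.2, step 3.11 (Visit 3) says that if the subject's "vision is unacceptable the subject will be discontinued".

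**The concern.** The purpose given in 14.9 is to judge the impact of subjects who leave. The set on which 14.1 would run that check contains only subjects who stayed, so the check and the population rule defeat each other.

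This matters more here than in a two-arm trial. The study is single-arm (4.1), and success means a confidence limit clearing a fixed value (14.5). If subjects who leave see worse than those who stay, the completers' mean is shifted towards success and no control arm carries a similar shift. The protocol makes such a link possible, because unacceptable vision is itself a ground for discontinuation and vision is what the primary endpoints measure.

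**Working it through.** **1. The passages side by side.**
- 14.9: impute to assess drop-out, if it exceeds 15%; population not stated.
- 14.1: all analyses per-protocol.
- 14.3: per-protocol means all visits completed.

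The number of drop-outs in the per-protocol set is therefore 0 at any drop-out rate. Imputation there could fill an isolated missing value in a completer, but nothing that is missing because a subject left.

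**2. Which values are really missing.** The primary CLUE score is the Visit 2 score (2.3, hypothesis 4; 14.5). CLUE and logMAR are recorded at steps 2.4 and 2.8. Step 3.11 comes one visit later. A subject stopped there already has observed Visit 2 values, which the per-protocol rule removes. Only subjects who leave before the Visit 2 measurements have truly missing Visit 2 data.

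**3. The plan's own figures.** Exact one-sample t-test power (two-sided 0.05) against 32 for CLUE, 0.10 for distance, and 0.17 for intermediate and near reproduces all nine rows in 14.2. For CLUE (SD 17), true values 38, 40 and 42 give 87, 50 and 33 subjects with power 0.902, 0.903 and 0.906. SD 17 and limit 32 are used below.

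**4. Where the trigger falls.** Assume 80 completers (the target), all in the per-protocol set. With all dispensed subjects as denominator, 14/94 = 14.9% triggers nothing and 15/95 = 15.8% is the first crossing. With the target of 80 as denominator, 12/80 = 15.0% does not trigger and 13/80 = 16.25% does.

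**5. Tipping point for CLUE (simple t interval).**

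Lowest completer mean that passes: 32 + t(0.975, 79) × 17/√80 = 32 + 3.78 = 35.78.

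Mean required over all 94: 32 + t(0.975, 93) × 17/√94 = 32 + 3.48 = 35.48.

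Drop-out mean at which the conclusion for all 94 reverses: (94 × 35.48 − 80 × completer mean)/14.

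| Completer mean | Completer lower limit | Reverses if drop-outs average at or below | Gap |
|---|---|---|---|
| 36 | 32.2 | (3335.1 − 2880)/14 = 32.5 | 3.5 points, 0.2 SD |
| 37 | 33.2 | (3335.1 − 2960)/14 = 26.8 | 10.2 points, 0.6 SD |
| 38 | 34.2 | (3335.1 − 3040)/14 = 21.1 | 16.9 points, 1.0 SD |
| 40 | 36.2 | (3335.1 − 3200)/14 = 9.7 | 30.3 points, 1.8 SD |

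Holding the SD at 17 ignores the extra spread from mixing two means. Allowing for it moves 21.1 to about 22.

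**6. False-success rate (20,000 simulated trials per setting).** Assumptions: true all-subject mean 32, SD 17 within groups, 14.9% drop-out, a Visit 2 score for everyone, and a chosen gap between completers and drop-outs. Completers-only analysis declares CLUE success in 2.4%, 11.8%, 25.4% and 49.0% of trials for gaps of 0, 10, 17 and 25 points. Using every Visit 2 score keeps it at 2.4% to 2.7%. At 16% drop-out, where the trigger is met, completers-only gives 12.7% and 28.9% for gaps of 10 and 17. At 5% drop-out it gives 4.6% and 6.4%.

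**The case against.** **ITT may have been intended.** Section 14.9 is a specific provision about drop-out, 14.1 is a general sentence, and the ITT set has no other use. A statistician could reasonably read the imputation as applying to ITT. That stands as a possible intention. The text never says it, though, and the wording of 14.1 admits no exception, so the population could be settled after the data are seen.

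**Other safeguards exist.** A reader might infer that 14.9 is the only protection against drop-out bias, or that the plan can detect nothing. The documents do not support that. Section 14.1 plans descriptive efficacy summaries for the Safety Population, which keeps anyone administered a lens with at least one observation. Missing counts and discontinuation reasons are recorded, and per-protocol exclusions for deviations are justified in a memo. These could reveal a gap between completers and drop-outs. What they do not do is test the success limits.

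**Step 3.11 does not make primary data missing.** Correct: those subjects have Visit 2 values. It is an argument for using the observed data, and should not be cited as proof that Visit 2 data are missing not at random.

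**The magnitude is assumed.** Also correct. Subjects are adapted monovision wearers who must find vision acceptable before dispensing, with up to two modifications allowed at Visit 1. Drop-out for unrelated reasons would narrow any gap. Nothing in the documents says drop-outs would score 21 or any other value.

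**Some remedies are preference.** At least 5 imputations already permits more, so the number is not a defect. A drop-out trigger is a design choice, but here it leaves up to 14 drop-outs among 94 without an inferential check.

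**Conclusion.** The point holds as a gap in specification: the one inferential drop-out check has no named population, and under 14.1 and 14.3 as written it has no drop-outs to work on. Observed Visit 2 primary values from subjects discontinued later go unused.

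The consequence depends on how close the result is. If completers average 36 on CLUE, 14 drop-outs only 3.5 points lower would reverse the conclusion for all 94. At 38 it takes a full SD, and at 40 nearly two. These figures rest on SD 17 from 14.2, 80 completers, assumed drop-out counts and means, and a simple t interval in place of the planned mixed model. They show that the check could matter, not that bias is expected. The sample-size figures in 14.2 are not in dispute. The change should be made before database lock. It does not require a different primary population.

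**What to change.** Amend 14.9, as a stated exception to 14.1:

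- **Population.** Run the sensitivity analysis on all subjects dispensed study lenses, and define that set explicitly. The ITT wording in 14.3 is broader because it is not limited to dispensed subjects, and the Safety Population includes anyone administered a lens, dispensed or not.
- **Trigger.** Run it whatever the drop-out rate. This also removes the undefined denominator.
- **Data.** Use all observed Visit 2 CLUE and logMAR values, including those of subjects discontinued later. Impute only values that are truly missing, from baseline and fitting data (for example habitual-lens CLUE, ADD power, refractive group and study-lens acuity at Visit 1).
- **Tipping point.** Regression imputation assumes missing at random, so add a simple delta step reporting how far drop-outs must fall below completers before each success limit in 14.5 is missed.

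The cost is a paragraph of SAP text and a few hours of programming on data already collected. Sample size, visits and clinical procedures do not change. The downside for the sponsor is that the sensitivity result may be less favourable than the per-protocol one.

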14.10. Procedure for Reporting Deviations from Statistical Plan

The analysis will be conducted according to that specified in above sections. There are no known reasons for which it is planned to deviate from these analysis methods. If for any reason a change is made, the change will be documented in the study report along with a justification for the change.

15. DATA HANDLING AND RECORD KEEPING/ARCHIVING

15.1. Electronic Case Report Form/Data Collection

The data for this study will be captured on electronic case report forms (eCRFs) using an EDC system (Bioclinica). An authorized data originator will enter study data into the eCRFs using the EDC system. Data collected on equipment that is not captured in EDC will be formatted to the specification of the JJV database manager and sent to JJV for analysis.

External Date Sources for this study include:

Not Applicable.

The clinical data will be recorded on dedicated eCRFs specifically designed to match the study procedures for each visit. Once completed, the eCRFs will be reviewed for accuracy and completeness and signed by the Investigator. The sponsor or sponsor's representatives

will be authorized to gain access to the subject recordation for the purposes of monitoring and auditing the study.

Edit checks, electronic queries, and audit trails are built into the system to ensure accurate and complete data collection. Data will be transmitted from the clinical site to a secure central database as forms are completed or updated, ensuring information accuracy, security, and confidentiality. After the final database lock, the Investigator will be provided with Individual Patient Profiles (IPP) including the full audit trail on electronic media in PDF format for all of the study data. The IPP must be retained in the study files as a certified copy of the source data for the study.

The content and structure of the eCRFs are compliant with ISO14155:2011.¹

15.2. Subject Record

At a minimum, subject record should be available for the following:

- subject identification
- eligibility
- study identification
- study discussion
- provision of and date of informed consent
- visit dates
- results of safety and efficacy parameters as required by the protocol
- a record of all adverse events
- follow-up of adverse events
- medical history and concomitant medication
- test article receipt/dispensing/return records
- date of study completion
- reason for early discontinuation of test article or withdrawal from the study, if applicable.

The subject record is the eCRF or an external record. The author of an entry in the subject record must be identifiable. The first point of entry is considered to be the source record.

Adverse event notes must be reviewed and initialed by the Investigator.

16. DATA MANAGEMENT

16.1. Access to Source Data/Document

The Investigator/Institution will permit trial-related monitoring, audits, IEC/IRB review and regulatory inspection(s) by providing direct access to source data/documents. Should the clinical site be contacted for an audit by an IEC/IRB or regulatory authority, JJV must be contacted and notified in writing within 24 hours.

16.2. Confidentiality of Information

Information concerning the investigational product and patent application processes, scientific data or other pertinent information is confidential and remains the property of JJV. The Investigator may use this information for the purposes of the study only. It is understood by the Investigator that JJV will use information developed in this clinical study in connection with the development of the investigational product and therefore may disclose it as required to other clinical investigators and to regulatory agencies. In order to allow the use of the information derived from this clinical study, the Investigator understands that he/she has an obligation to provide complete test results and all data developed during this study to the Sponsor.

16.3. Data Quality Assurance

Steps will be taken to ensure the accuracy and reliability of data, include the selection of qualified investigators and appropriate clinical sites and review of protocol procedures with the Principal Investigator. The Principal Investigator, in turn, must ensure that all Sub-Investigators and clinical site personnel are familiar with the protocol and all study-specific procedures and have appropriate knowledge of the study article.

Training on case report form completion will be provided to clinical site personnel before the start of the study. The Sponsor will review case report forms for accuracy and completeness remotely during the conduct of the study, during monitoring visits, and after transmission to data management. Any data discrepancies will be resolved with the Investigator or designee, as appropriate.

Quality Assurance representatives from JJV may visit clinical sites to review data produced during the study and to access compliance with applicable regulations pertaining to the conduct of clinical trials. The clinical sites will provide direct access to study-related source data/documents and reports for the purpose of monitoring and auditing by JJV and for inspection by local and regulatory authorities.

17. MONITORING

The study monitors will maintain close contact with the Principal Investigator and the Investigator's designated clinical site personnel. The monitor's responsibilities will include:

- Ensuring that the investigation is being conducted according to the protocol, any subsequent amendments, and regulatory requirements are maintained
- Ensuring the rights and wellbeing of subjects are protected
- Ensuring adequate resources, including facilities, laboratories, equipment, and qualified clinical site personnel
- Ensuring that protocol deviations are documented with corrective action plans, as applicable
- Ensuring that the clinical site has sufficient test article and supplies
- Clarifying questions regarding the study
- Resolving study issues or problems that may arise

- Reviewing of study records and source documentation verification in accordance with the monitoring plan.

18. ETHICAL AND REGULATORY ASPECTS

18.1. Study-Specific Design Considerations

Potential subjects will be fully informed of the risks and requirements of the study and, during the study, subjects will be given any new information that may affect their decision to continue participation. Subjects will be told that their consent to participate in the study is voluntary and may be withdrawn at any time with no reason given and without penalty or loss of benefits to which they would otherwise be entitled. Only subjects who are fully able to understand the risks, benefits, and potential adverse events of the study, and provide their consent voluntarily will be enrolled.

18.2. Investigator Responsibility

The Principal Investigator is responsible for ensuring that the clinical study is performed in accordance with the signed agreement, the investigational plan, Section 4 of the ICH E6 guidelines on Good Clinical Practice (GCP),² and applicable regulatory requirements. GCP is an international ethical and scientific quality standard for designing, conducting, recording, and reporting studies that involve the participation of human subjects. Compliance with this standard provides public assurance that the rights, safety, and well-being of study subjects are protected, consistent with the principles of the Declaration of Helsinki 64th WMA General Assembly 2013³ and that the clinical study data are credible. The Investigator must maintain clinical study files in accordance with Section 8 of the ICH E6 guidelines on Good Clinical Practice (GCP),² and applicable regulatory requirements.

18.3. Independent Ethics Committee or Institutional Review Board (IEC/IRB)

Before the start of the study, the Investigator (or Sponsor when applicable) will provide the IEC/IRB with current and complete copies of the following documents (where applicable):

- Final protocol and, if applicable, amendments
- Sponsor-approved informed consent form (and any other written materials to be provided to the subjects)
- Investigator's Brochure (or equivalent information) and amendments
- Sponsor-approved subject recruitment materials
- Information on compensation for study-related injuries or payment to subjects for participation in the study
- Investigator's curriculum vitae, clinical licenses, or equivalent information (unless not required, as documented by IEC/IRB)
- Information regarding funding, name of the Sponsor, institutional affiliations, other potential conflicts of interest, and incentives for subjects
- Any other documents that the IEC/IRB requests to fulfill its obligation.

This study will be undertaken only after IEC/IRB has given full approval of the final protocol, amendments (if any), the informed consent form, applicable recruiting materials,

and subject compensation programs, and the Sponsor has received a copy of this approval. This approval letter must be dated and must clearly identify the documents being approved.

During the study, the Investigator (or Sponsor when applicable) will send the following documents to the IEC/IRB for their review and approval, where appropriate:

- Protocol amendments
- Revision(s) to informed consent form and any other written materials to be provided to subjects
- If applicable, new or revised subject recruitment materials approved by the Sponsor
- Revisions to compensation for study-related injuries or payment to subjects for participation in the study
- Investigator's Brochure amendments or new edition(s)
- Summaries of the status of the study (at least annually or at intervals stipulated in guidelines of the IEC/IRB)
- Reports of adverse events that are serious, unanticipated, and associated with the test articles, according to the IRB's requirements
- New information that may adversely affect the safety of the subjects or the conduct of the study
- Major protocol deviations as required by the IEC/IRB
- Report of deaths of subjects under the Investigator's care
- Notification if a new Investigator is responsible for the study at the clinical site
- Any other requirements of the IEC/IRB.

For protocol amendments that increase subject risk, the amendment and applicable informed consent form revisions must be submitted promptly to the IEC/IRB for review and approval before implementation of the change(s).

At least once a year, the IEC/IRB will review and reapprove this clinical study. This request should be documented in writing.

At the end of the study, the Investigator (or Sponsor where required) will notify the IEC/IRB about the study completion. Documentation of this notification must be retained at the clinical site and a copy provided to the CRO or Sponsor as applicable.

